## Participants.

Participants will be 60 7- to 11-year-olds with ASD: 30 will be randomly assigned to training and 30 to waitlist. It is anticipated that 80 children with ASD will be recruited to obtain a final sample with artifact free data.

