Mind Test. These tasks allow for sufficient variability to detect individual differences at the planned age range. Parent and teacher report of social function and social symptoms will be collected via the Social Skills Improvement System and Social Responsiveness Scale-2, respectively.

*Aim 3 behavioral assessment.* Data will be collected before and after training with the same battery of tasks. In addition to ERP (Child ANT, Go/Nogo), the behavioral assessment battery will include executive control measures (Stroop, Change Task, and Hungry Donkey Task) and a brief (non-conflict) task (Backward Digit Span). Parent and teacher report of executive function will also be collected at baseline using the BRIEF questionnaire. At post-testing, ERP, behavioral measures of executive control and parent/teacher report of executive control will be collected again. TOM tasks (SAT, Perception Knowledge, False Belief tasks, and the TOM Test) as well as parent and teacher report measures (SSIS, SRS) will also be collected. Results from Aims 1-2 will be used to further inform decisions about which measures to prioritize in post-training testing, which will be important for obtaining artifact free ERP data from the majority of children with ASD across time points.

Summary of measures in Electrophysiological and Behavioral Battery with children with ASD

Construct and Type	Measure Name and Citation
Autism Symptoms-Diagnosis	Autism Diagnostic Observation Schedule-2 (ADOS-2)
Autism Symptoms-Diagnosis	Autism Diagnostic Interview-Revised (ADI-R)
Intelligence/Verbal Intelligence	Wechsler Abbreviated Scale of Intelligence-2 (WASI-2)
Conflict Processing-ERP	Cued Go/Nogo
Conflict Processing-ERP	Child Attention Network Task (Child ANT)
Conflict Processing	Hungry Donkey Task
Conflict Processing	Change Task
Conflict Processing	Stroop Task
Exec. Control at home/school	BRIEF Parent and Teacher Surveys
Theory of Mind	Social Attribution Task (SAT)
Theory of Mind	Perception Knowledge
Theory of Mind	Location Change False Belief
Theory of Mind	Unexpected-contents False Belief
Theory of Mind	TOM Test
Social function at home/school	Social Skills Improvement System-Parent & Teacher Surveys (SSIS)
Social symptoms home/school	Social Responsiveness Scale-Parent & Teacher Surveys (SRS)
*Working Memory	Backward Digit Span

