Note: Measures with \* will serve as contrasts to Executive Control Measures for Brain-Behavior comparisons. *Italicized measures are parent report.*

**Intervention: Brief computerized executive control training.** Children with ASD will be randomly assigned to either computer training or a waitlist control condition following a list generated by a staff member independent of the research team using a computer algorithm to generate a random order. Training designed to directly target executive control and attention will follow the basic protocol used with TD children. Ten training visits will occur over a 2-3-month period. A research assistant or graduate student will conduct visits, so the assessment team may remain naïve to treatment status. *Four training exercises* appropriate for typically developing children 6 years and older will be used, including anticipation, stimulus discrimination, conflict resolution, and inhibition tasks. *Criteria for progress* throughout each level are based on the number of consecutive correct responses. Our current pilot study is evaluating the optimal duration. In more recent work, Rueda and her colleagues have used a 10-hour training protocol instead of a 5-hour protocol. Based on our current piloting, we plan to deliver the same duration of training to each participant, such that if children with ASD pass all training activities a shorter duration, additional training will be provided in conflict resolution and inhibition tasks until the training hours are completed. Both groups will return to the lab for follow-up testing 2-3 months after baseline assessment, after which the waitlist group will be offered training if it is efficacious. *Training modifications* will be made following piloting if needed and may include: allowing

children to pick characters that are highly motivating, reducing language demands, and extending tasks for older children.

*Attrition* will be addressed by recruiting additional participants. Attrition is expected to be very low, given 0% attrition with similar, brief computer training for individuals with ASD.

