### Statistical Analyses.

To assess potential training effects on ERP components, repeated-measures ANCOVA will be calculated by comparing groups (trained/waitlist) and within subjects effects of condition (congruent/ incongruent or Go/Nogo) and time point (baseline/post treatment) and number of trials covaried. ANCOVA controlling for baseline performance will be used to test executive control behavior (Hungry Donkey, Stroop, Change Task) and parent/teacher BRIEF scores pre/post training. Second, to test generalization of training to social measures, ANCOVA controlling for baseline will be used to assess differences in social cognition (TOM composite), social function (SSIS), and social symptoms (SRS). As a control condition, ANCOVA will also be used to measure potential changes with a non-conflict task (Backward Digit Span). *Power:* Given the proposed sample size of 30 children per group and a correlation of 0.3 or greater, with power of 0.8 and alpha = 0.05, a moderate effect size ( $f^2 = 0.21$ ) would be detected via repeated measures ANCOVA. ANCOVA with 1 covariate will have 0.8 power to detect a large effect size ( $f^2 = 0.37$ ) for behavioral and parent report tasks after training.

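### No group × task contrast is specified for the behavioral outcomes, so a claim that training gains are specific to conflict tasks would rest on comparing separate p-values

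*Combined protocol and SAP*

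**What the plan says.** The Statistical Analyses section sets out the behavioral tests one outcome at a time. For the conflict tasks, "ANCOVA controlling for baseline performance will be used to test executive control behavior (Hungry Donkey, Stroop, Change Task"), along with the BRIEF. For the comparison task, "As a control condition, ANCOVA will also be used to measure potential changes with a non-conflict task (Backward Digit Span"). It gives no term, margin or rule for comparing the training effect on one kind of task with the effect on the other.

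Backward Digit Span belongs to the Aim 3 battery given before and after training, described there as "and a brief (non-conflict) task (Backward Digit Span"). In the summary table of measures it is the only starred row, under the construct "Working Memory". The note to that table says starred measures "will serve as contrasts to Executive Control Measures for Brain-Behavior comparisons".

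The ERP model is built differently. It compares the groups with "within subjects effects of condition (congruent/ incongruent or Go/Nogo) and time point (baseline/post treatment"), so condition is a factor inside the model.

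**The concern.** A control outcome is informative through its relation to the target outcomes. If the conflict tasks improve and digit span does not, the natural reading is that training acts on conflict processing and not on test performance in general. As planned, that reading would come from setting separate p-values side by side. One test can be significant and another not when the two effects are identical, and this is common when each test has moderate power.

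The design makes the distinction worth having. Trained children attend ten visits with a research assistant or graduate student, while waitlisted children attend none in that period. Contact, practice at computer tasks and motivation are therefore live explanations for a general gain. Among the behavioral outcomes, digit span is the only one labelled as a control.

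**Working it through.** **Inputs from the documents.** Allocation: "30 will be randomly assigned to training and 30 to waitlist" (Participants). Power statement: "with power of 0.8 and alpha = 0.05" (Statistical Analyses), with a detectable effect of 0.37 for an ANCOVA with one covariate. Sidedness is not stated; an F test, equivalent to a two-sided t test, is used here.

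**Assumed.** The residual correlation r between tasks after baseline adjustment is not in the documents; 0.2, 0.3 and 0.5 are used. Effects are in residual SD units.

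**Step 1: the plan's own figure.** Noncentral F with 1 and 57 df and λ = f² × 60. With f = 0.37, λ = 0.1369 × 60 = 8.21 and power is 0.804, which matches the stated 0.8. Taking 0.37 literally as f², as labelled, gives λ = 22.2 and power 0.996. The figure therefore behaves as Cohen's f, which is d = 2 × 0.37 = 0.74.

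**Step 2: power of the digit-span ANCOVA.** At d = 0.5, f = 0.25, λ = 0.0625 × 60 = 3.75 and power is 0.478. If digit span truly improves by 0.5 SD, a null result is slightly more likely than not.

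**Step 3: how often equal effects look specific.** With independent tasks and one named conflict task at d = 0.5, the chance is 0.478 × (1 − 0.478) = 0.25. Correlated tasks were simulated: 30 per group, four tasks with the same true effect, unit residual SD, common correlation r and 40,000 trials per setting. Adjusted scores were compared by t test on 58 df, which is practically the same as 57. The pattern counted is a significant improvement on the conflict task(s) with digit span not significant. At d = 0.5:

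| Conflict tasks required to be significant | r = 0.2 | r = 0.3 | r = 0.5 |
|---|---|---|---|
| One named in advance | 22.0% | 20.2% | 16.9% |
| At least one of three | 39.5% | 36.6% | 30.7% |
| At least two of three | 20.4% | 18.5% | 15.1% |
| All three | 5.7% | 5.5% | 4.9% |

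For at least one of three, the range is 25–33% at d = 0.3 and 16–19% at d = 0.74.

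**Step 4: the direct contrast.** Take the mean of the three conflict scores minus digit span. Its variance per child is v = (1 − r)(1 + 1/3), and λ = 15δ²/v, where 15 = 30/2 and δ is the differential effect. Under equal effects it rejects in about 5% of trials, about 2.5% in the favorable direction.

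| True effects | r | v | λ | Power |
|---|---|---|---|---|
| 0.74 versus 0 | 0.2 | 1.067 | 8.21/1.067 = 7.70 | 78% |
| 0.74 versus 0 | 0.5 | 0.667 | 8.21/0.667 = 12.3 | 93% |
| 0.5 versus 0 | 0.2 | 1.067 | 3.75/1.067 = 3.52 | 45% |
| 0.5 versus 0 | 0.5 | 0.667 | 3.75/0.667 = 5.63 | 65% |

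A contrast using a single conflict task has v = 2 − 2r. Its power at 0.74 versus 0 is lower: 66% at r = 0.3 and 80% at r = 0.5.

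**The case against.** Four objections carry weight.

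- **The ERP model.** A reader might infer that the plan cannot show specificity at all. The documents do not support that. Group × condition × time tests whether training changes the conflict condition more than the non-conflict condition, in the same child and task. This stands and limits the point to the behavioral outcomes. It does not fill the behavioral gap, because those outcomes are different and digit span is not in that model.
- **The note on starred measures.** A reader might infer that the plan promises this contrast and then omits it. The note confines the contrast role to brain-behavior comparisons, which is a different purpose, so it cannot be cited as a promise of a group × task test.
- **No stated inference.** Specificity is not a formal hypothesis, and nothing says that a digit-span null will be read as specificity. A significant digit-span gain would be a useful warning of a general effect without any comparison of p-values. This stands. Specificity is implied only by the control label. However, a null on digit span is the result that invites the reading, and the plan offers no better tool for it.
- **The choice of pattern.** The 31–40% figure comes from the most permissive rule, and the plan states no rule. A stricter rule lowers the figure to 17–22% for one named task and to about 5% for all three. All of these should be shown together.

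The contrast also has limits. It pools three different tasks into one level, and a standardized difference in effects can be created or hidden by unequal task reliability.

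**Conclusion.** The point holds for the behavioral outcomes only. The control task and the conflict tasks are analyzed separately and no comparison of their training effects is specified, so the analysis as written gives no valid test of behavioral specificity. The tests of training effect on each task are unaffected.

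With 30 per group and a common 0.5 SD effect, separate tests would make a general gain look specific in about one trial in five for a named conflict task. The range runs from about 5% to 40% with the number of conflict tasks required. These figures rest on equal effects across tasks and on residual correlations of 0.2 to 0.5, which are assumptions. The 48% power of the digit-span ANCOVA at 0.5 SD needs no between-task correlation.

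The gap is one of analysis, not design, and can be repaired at low cost.

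**What to change.** Pre-specify one model for the post-test scores of Stroop, Change Task, Hungry Donkey and Backward Digit Span. Standardize the scores and sign them so that higher is better. Adjust for each task's baseline, include child as a random effect, and fit group × task type (conflict versus non-conflict). Report the interaction with its confidence interval, and base any behavioral specificity claim on it and not on a digit-span null. Keep the separate digit-span ANCOVA as descriptive, with its interval. If the sponsor does not want this model, the alternative is to state that no behavioral specificity claim will be made.

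The cost is one extra model, with no new visits or participants. It does require digit span to be kept at post-test; the Aim 3 section leaves room to prioritize measures at that point.

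The plan should state two downsides. Power is 78–93% for 0.74 SD versus 0 but only 45–65% for 0.5 SD versus 0, so a non-significant interaction is inconclusive. The standardized contrast also assumes broadly similar reliability across tasks; the waitlist group's pre/post correlations on each task would help the reader to judge that.

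### The ANCOVA power statement prints 0.37 as f² when the stated inputs give f = 0.37 (f² = 0.135); the repeated-measures figure of 0.21 is under-specified and should be checked for the same slip

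*Combined protocol and SAP*

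**What the plan says.** Two effect sizes appear in the power paragraph at the end of Statistical Analyses.

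- **ANCOVA**, for the behavioural and parent-report outcomes after training: "ANCOVA with 1 covariate will have 0.8 power to detect a large effect size ( $f^2 = 0.37").
- **Repeated-measures ANCOVA**, for the ERP components: "with power of 0.8 and alpha = 0.05, a moderate effect size ( $f^2 = 0.21$ ) would be detected".

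The stated inputs are "Given the proposed sample size of 30 children per group and a correlation of 0.3 or greater", power 0.8 and alpha 0.05. The Participants section gives the same allocation: "30 will be randomly assigned to training and 30 to waitlist", so N = 60.

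The ERP model compares the two groups and includes "within subjects effects of condition (congruent/ incongruent or Go/Nogo) and time point (baseline/post treatment) and number of trials covaried". The paragraph does not say which term of that model the 0.21 refers to, how many measurements were assumed, which correlation is meant, or how the effect size is defined. It names no software.

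**The concern.** Cohen's f and f² are different scales, and a value such as 0.37 means very different things on each. For two equal groups the standardised difference is 2f. So f = 0.37 is a difference of 0.74 residual SD, while f² = 0.37 means f = 0.608 and a difference of 1.22 residual SD. A difference of 1.22 SD is far larger than a two-group comparison with 30 per arm normally needs for 80% power, which suggests that the symbol is wrong.

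These two figures are the plan's only statement of what 30 children per group can detect. A reader who takes f² = 0.37 literally would conclude that the behavioural and parent-report analyses can find only very large effects. That would mislead anyone interpreting a null result or reusing the figure to plan a later trial.

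**Working it through.** **Inputs.** N = 60, 30 per group (Participants; Statistical Analyses). Alpha 0.05, power 0.8, one covariate, correlation 0.3 or more (Statistical Analyses). All calculations use the noncentral F distribution.

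**1. ANCOVA, two groups, one covariate**

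Numerator df = 1; error df = N − 3 = 57; noncentrality λ = f² × N.

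- The plan's figure as printed, f² = 0.37: λ = 0.37 × 60 = 22.2; power = 99.6%. It does not reproduce.
- The same number read as f: f² = 0.37² = 0.1369; λ = 0.1369 × 60 = 8.21; power = 80.4%. It reproduces.
- Solving for 80% power: λ = 8.122; f² = 8.122 / 60 = 0.135; f = 0.368; difference = 2 × 0.368 = 0.74 residual SD.
- Size of the discrepancy: 0.37 / 0.135 = 2.7 on the f² scale.

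Solving for sample size (balanced total, error df N − 3):

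| 0.37 read as | Smallest total N for 80% power | Power at that N | Power at N − 2 |
|---|---|---|---|
| f² | 24 | 81.1% | 77.2% |
| f | 60 | 80.4% | 79.1% |

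Two other readings do not rescue f² = 0.37. Alpha 0.10, as a one-sided equivalent, raises power at f² = 0.37 to 99.9%. Splitting alpha over 3, 5 or 10 outcomes gives detectable f² of 0.18, 0.21 or 0.24.

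**2. Repeated-measures figure**

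The term is not named, so several versions were tried at correlation ρ = 0.3, with m measurements. Where the correlation enters the noncentrality:

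- group-by-time (interaction): λ = f² × 60m / (1 − ρ)
- between groups: λ = f² × 60m / (1 + (m − 1)ρ)

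| Version | Detectable f² (f) at 80% power | Power at f² = 0.21 |
|---|---|---|
| m = 2, interaction, 1 df | 0.047 (0.218) | >99.9% |
| m = 2, between groups | 0.088 (0.297) | 99.1% |
| m = 4, interaction, 1 df | 0.024 (0.154) | >99.9% |
| m = 4, interaction, 3 df | 0.033 (0.180) | >99.9% |
| m = 4, between groups | 0.064 (0.253) | 99.9% |
| m = 2, 1 df, correlation not used, λ = f² × 58 | 0.140 (0.374) | 92.9% |
| 3-df multivariate test, correlation not used, λ = f² × 56 | 0.209 | 80.2% |
| 3-df multivariate test, correlation not used, λ = f² × 58 | 0.202 | 81.8% |

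The last two rows use df 3 and 56, and they do agree with f² = 0.21.

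Read as f instead, 0.21 in the two-measurement group-by-time test gives λ = 0.0441 × 120 / (1 − ρ). At ρ = 0.30, λ = 7.56 and power is 77.2%. At ρ = 0.35, λ = 8.14 and power is 80.1%.

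**The case against.** The strongest objection concerns the repeated-measures figure. Having seen the ANCOVA slip, a reader might infer that f² = 0.21 is wrong in the same way. The documents do not support that, for two reasons.

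- A 3-df multivariate convention gives 80 to 82% power at f² = 0.21 as printed. It is weak evidence of what was done, because it makes no use of the stated correlation, and the group-by-time terms on two-level factors have 1 df. It still rules out saying that the figure cannot be reproduced.
- Read as f, 0.21 misses slightly at correlation 0.30 (77.2%) but reaches 80.1% at 0.35, and the plan's wording, "a correlation of 0.3 or greater", allows 0.35.

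So 0.21 has two partial explanations, one on each scale. What can be shown is that the figure is under-specified.

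A second objection is that little hangs on this. That stands. The ANCOVA calculation itself appears sound, because 0.37 as f fits N = 60 exactly and only the label is wrong. The error is conservative, and no sample size, analysis or decision rule in the documents depends on either figure.

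The words "moderate" and "large" are not part of this point. The plan names no benchmark for them, so they cannot be shown to be wrong from the documents.

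**Conclusion.** The ANCOVA statement is wrong as written, with high confidence. On the plan's own inputs the effect detectable with 80% power is f² = 0.135, not 0.37, or about 0.74 residual SD and not 1.22. That f was printed as f² is an inference from the numerical match, because the plan gives neither software nor definition. The failure of the printed statement does not rest on that inference. It rests only on a standard two-group ANCOVA F test with 30 analysed per group.

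A reader might also infer that the trial is underpowered, or that it can detect only very large effects. The arithmetic points the other way: the text understates the trial's sensitivity.

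The repeated-measures figure is an open question, held with less confidence. It does not match the planned 1-df group-by-time tests at correlation 0.3, but the versions tried do not exhaust the possible definitions and the documents do not settle which was used.

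Overall severity: minor.

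**What to change.** 1. Replace the ANCOVA sentence with: With 30 per group, alpha 0.05 and one covariate, ANCOVA has 80% power for f = 0.37 (f² = 0.135), an adjusted group difference of about 0.74 residual SD.
2. Go back to the repeated-measures calculation and check whether 0.21 is also f. Restate it with the model term tested, the number of measurements, the correlation used, and the effect-size definition (f or f², and whether the correlation is included in it).

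The cost is a change of wording and numbers in two sentences of the power paragraph, plus retrieving or rerunning one calculation. The sample size, design and analyses do not change.
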